4 STUDY DESIGN

- Study population and groups: those patients on haemodynamic monitoring in ICU (PiCCO monitoring)
- **Calculation of the sample size:**

Taking into account that the primary objective of the study is to analyze the relationship between the quantitative variables: change in pH and change in Cardiac Contractility, assuming an alpha risk of 5% (95% confidence level), a 20% beta risk (power of 80%) and a minimum ratio that has an estimated clinical significance with a correlation coefficient of 1.5, a bilateral estimate of sample size of 346 subjects is obtained. Assuming a 5% loss (17 individuals) during the study a total of 363 cases would be necessary.

- **Statistical methods:**

The description of quantitative variables is carried out with central tendency and dispersion indices, whether based on values (mean and standard deviation) or on ordinations (median and interquartile range) according to whether they meet normality or not, respectively. Its graphic representation is done with Histograms and Cash Diagrams. The description of categorical variables is performed with absolute and relative frequencies in percentages. Its graphic representation is done with bar charts.

Full title of the research: **The impact of systemic pH on cardiac function and clinical outcome in the critically ill patient.**

IRAS Project ID: **227870**

The relationship between categorical variables is analyzed by comparing proportions with the Pearson Chi-square test, provided that there are less than 20% of squares in the contingency table with expected frequencies less than 5. In the case that there is more 20% of squares with expected frequencies less than 5, the Fisher's exact test is used bilaterally.

The magnitude of the effect of the relationship between two binary variables has been analyzed with the Ratios of proportions or Relative Risk and with the Odds Ratio.

The relationship between a binary exposure variable and a quantitative response is analyzed with the Student-Fisher t test for independent samples if the normality condition is met. According to whether or not the equality of variances are met, the Student-Fisher t test is used for independent groups for homogeneous variances or for non-homogeneous variances, respectively. In case of not fulfilling the condition of normality, the comparison of two means is made with the non-parametric Mann-Whitney U test.

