The comparison between a polytomic predictor and a quantitative response is made through the analysis of variance (ANOVA) in the case of meeting the conditions of normality and homogeneity of variances. If any of these conditions is not met, it is done with the non-parametric H test of Kruskal-Wallis. If the polytomic predictor is ordinal, the ANOVA trend test or the non-parametric Jonckheere-Terpstra trend test is also used, depending on whether normality is met or not, respectively.

Full title of the research: **The impact of systemic pH on cardiac function and clinical outcome in the critically ill patient.**

IRAS Project ID: **227870**

The relationship between two independent quantitative variables is evaluated with the correlation coefficient r of Pearson if normality is met, or with the nonparametric correlation coefficient ρ of Spearman if normality is not met. Its graphic representation is made with the scatter diagrams or points.

Normality is assessed with the Kolmogorov-Smirnov test with the Lilliefors significance correction for large samples, or with the Shapiro-Wilks test for small samples. The equality of variances is analyzed with the Levene variance homogeneity test.

The relationship between two related quantitative variables is performed using the Student-Fisher t-test for related samples in case the normality condition is met. Otherwise, the non-parametric Wilcoxon T test is used. The relationship between two paired categorical variables is performed by the McNemar symmetry test.

The relationship between a continuous quantitative response and one or several predictors, whether binary, polytomic or quantitative, is done with Simple or Multiple Linear Regression respectively.

The polytomous predictors variables are introduced in the Linear Regression models broken down into binary indicator variables coded with respect to the first reference category.

An estimative multivariate linear regression model of the effect of the predictor Change of pH (between the lowest and highest pH) on the response Change in cardiac output

Full title of the research: **The impact of systemic pH on cardiac function and clinical outcome in the critically ill patient.**

IRAS Project ID: **227870**

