8 STATISTICAL METHODS

The description of quantitative variables is carried out with central tendency and dispersion indices, whether based on values (mean and standard deviation) or on ordinations (median and interquartile range) according to whether they meet normality or not, respectively. Its graphic representation is done with Histograms and Cash Diagrams. The description of categorical variables is performed with absolute and relative frequencies in percentages. Its graphic representation is done with bar charts.

The relationship between categorical variables is analyzed by comparing proportions with the Pearson Chi-square test, provided that there are less than 20% of squares in the contingency table with expected frequencies less than 5. In the case that there is more 20% of squares with expected frequencies less than 5, the Fisher's exact test is used bilaterally.

Full title of the research: **The impact of systemic pH on cardiac function and clinical outcome in the critically ill patient.**

IRAS Project ID: **227870**

The magnitude of the effect of the relationship between two binary variables has been analyzed with the Ratios of proportions or Relative Risk and with the Odds Ratio.

The relationship between a binary exposure variable and a quantitative response is analyzed with the Student-Fisher t test for independent samples if the normality condition is met. According to whether or not the equality of variances are met, the Student-Fisher t test is used for independent groups for homogeneous variances or for non-homogeneous variances, respectively. In case of not fulfilling the condition of normality, the comparison of two means is made with the non-parametric Mann-Whitney U test.

The comparison between a polytomic predictor and a quantitative response is made through the analysis of variance (ANOVA) in the case of meeting the conditions of normality and homogeneity of variances. If any of these conditions is not met, it is done with the non-parametric H test of Kruskal-Wallis. If the polytomic predictor is ordinal, the ANOVA trend test or the non-parametric Jonckheere-Terpstra trend test is also used, depending on whether normality is met or not, respectively.

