The relationship between two independent quantitative variables is evaluated with the correlation coefficient r of Pearson if normality is met, or with the nonparametric correlation coefficient ρ of Spearman if normality is not met. Its graphic representation is made with the scatter diagrams or points.

Full title of the research: **The impact of systemic pH on cardiac function and clinical outcome in the critically ill patient.**

IRAS Project ID: **227870**

Normality is assessed with the Kolmogorov-Smirnov test with the Lilliefors significance correction for large samples, or with the Shapiro-Wilks test for small samples. The equality of variances is analyzed with the Levene variance homogeneity test.

The relationship between two related quantitative variables is performed using the Student-Fisher t-test for related samples in case the normality condition is met. Otherwise, the non-parametric Wilcoxon T test is used. The relationship between two paired categorical variables is performed by the McNemar symmetry test.

The relationship between a continuous quantitative response and one or several predictors, whether binary, polytomic or quantitative, is done with Simple or Multiple Linear Regression respectively.

The polytomous predictors variables are introduced in the Linear Regression models broken down into binary indicator variables coded with respect to the first reference category.

An estimative multivariate linear regression model of the effect of the predictor Change of pH (between the lowest and highest pH) on the response Change in cardiac output (corresponding to the moments between the lowest and the highest pH) has been performed. The possible role as confounding factors of several variables on this relationship has been evaluated. A predictive multivariate model of linear regression has been performed to evaluate the factors that intervene in the Cardiac Contractility.

Full title of the research: **The impact of systemic pH on cardiac function and clinical outcome in the critically ill patient.**

IRAS Project ID: **227870**

Both the predictive and the estimative models have been carried out with the manual backward step procedure using the criterion of decreasing statistical significance to establish the order to evaluate the withdrawal or permanence of each predictor.

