In the multivariate predictive linear regression model, the criterion of statistical significance was used to decide the maintenance or withdrawal of the predictors in each step. They remain in the model if they are significant and are removed from the model if they are not significant.

In the multivariate models of linear regression, the criterion of clinical significance has been used to decide on the maintenance or withdrawal of the predictors in each step. They remain in the model if they produce a change greater than 10% in the coefficient of the predictor of interest (presence of confounding bias) and withdraw if the change is less than 10% (absence of confounding bias).

The conditions of application of the simple or multiple linear regression (linearity, independence, normality and equality of variances) are evaluated by analysing the residuals.

Values of $P < 0.05$ are considered significant. The statistical treatment has been performed the statistical package SPSS, version 18 (SPSS Inc, Chicago, IL, USA).

Full title of the research: **The impact of systemic pH on cardiac function and clinical outcome in the critically ill patient.**

IRAS Project ID: **227870**

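### The supplementary trend test for ordered groups is chosen on normality alone, so data that fail the plan's equal-variance condition for ANOVA still get the ANOVA trend test

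*Combined protocol and SAP*

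**What the plan says.** For a quantitative response and a predictor with three or more categories, section 8 uses ANOVA "in the case of meeting the conditions of normality and homogeneity of variances". It then adds: "If any of these conditions is not met, it is done with the non-parametric H test of Kruskal-Wallis". The next sentence covers ordered categories: "the ANOVA trend test or the non-parametric Jonckheere-Terpstra trend test is also used, depending on whether normality is met or not". Variance is not mentioned there. The same wording stands in section 4 ("If the polytomic predictor is ordinal, the ANOVA trend test") and in the statistical methodology row of the Study Summary.

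Two neighbouring rules matter. The two-group comparison has a branch for unequal spread: "the Student-Fisher t test is used for independent groups for homogeneous variances or for non-homogeneous variances, respectively". A variance check is also planned: "The equality of variances is analyzed with the Levene variance homogeneity test". Neither is tied to the trend test. The significance rule is "Values of $P < 0.05$ are considered significant".

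**The concern.** Take ordered groups with normal data and a failed Levene test. Under the plan, the overall comparison goes to Kruskal-Wallis because the pooled variance cannot be trusted. The trend comparison on the same data goes to the ANOVA trend test, which normally uses that pooled variance. The plan would detect the problem in one sentence and disregard it in the next.

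What is at stake is the error rate of any trend P value reported this way. If the smaller groups are the more variable, the pooled variance understates the uncertainty of the contrast and false trends exceed 5%. If the larger groups are the more variable, it overstates the uncertainty and real trends are missed. The study is observational, so nothing in the design balances group sizes.

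**Working it through.** **Inputs from the documents.** Significance level 0.05 (section 8) and N = 346 before losses (section 4). The plan states no error rate for the trend test other than the nominal one. Its own N can be reproduced with the Fisher-z formula, two-sided, 80% power, r = 0.15: ((1.960 + 0.842)/atanh(0.15))² + 3 = (2.802/0.1511)² + 3 ≈ 346.6. The printed correlation of 1.5 is impossible; that is a separate matter and does not affect this point.

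**Assumptions.** Group sizes and SDs, because the documents give none; normal data; no true differences in means; and a pooled error term, which is inferred from the name of the test.

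**Formula.** For contrast weights c, group sizes n and SDs σ over k groups:

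- true variance V = Σ c²σ²/n
- pooled variance S² = Σ (n − 1)σ²/(N − k)
- variance used by the test P = S² Σ c²/n
- R = V/P, and actual error ≈ 2[1 − Φ(t/√R)], with t = 1.967 the 97.5% point on N − k degrees of freedom

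**Worked case: sizes 200/100/46, SDs 1/1.5/2, c = (−1, 0, 1).**

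- V = 1/200 + 4/46 = 0.09196
- S² = (199 × 1 + 99 × 2.25 + 45 × 4)/343 = 601.75/343 = 1.7544
- P = 1.7544 × (1/200 + 1/46) = 0.04691
- R = 1.960, √R = 1.400, and 1.967/1.400 = 1.405, so the error is 16.0%

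The sample-size-weighted linear term uses c = n(x − x̄), with scores x = 0, 1, 2 and x̄ = 192/346 = 0.555. It gives R = 1.575 and 11.7%.

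**Same calculation, other assumed patterns (all N = 346).**

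| Sizes | SDs | R, unweighted | Error, unweighted | Error, n-weighted |
|---|---|---|---|---|
| 200/100/46 | 1/1.25/1.5 | 1.520 | 11.1% | 8.6% |
| 200/100/46 | 1/1.5/2 | 1.960 | 16.0% | 11.7% |
| 180/90/50/26 | 1/1.5/2/2.5 | 2.537 | 21.7% | 14.4% |
| 46/100/200 | 1/1.5/2 | 0.503 | 0.6% | 1.9% |
| 115/115/116 | 1/1.5/2 | 1.030 | 5.3% | 5.3% |
| 115/115/116 | 2/1/2 | 1.332 | 8.8% | 8.8% |
| 115/115/116 | 1/2/1 | 0.501 | 0.5% | 0.5% |

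Simulation agrees closely. Over a wider set of sizes and SDs the unweighted error ran from about 0.2% to 28%. Equal group sizes do not guarantee 5%: the result then depends on whether the outer or the middle groups are the more variable.

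**Does the plan's own check see it?** With sizes 200/100/46 and the smaller groups more variable, Levene's test rejects in 91–100% of samples.

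**Effect of the normality test.** The plan sends non-normal data to Jonckheere-Terpstra, and pooling groups of unequal spread can itself look non-normal. With that gate simulated for the first three rows of the table (unweighted contrast), the error of the whole procedure is 10.7%, 12.9% and 12.1% if normality is tested on the whole response, and 10.8%, 15.9% and 19.2% if it is tested within each group. The plan does not say which applies.

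**Candidate remedies.** A separate-variance contrast with Satterthwaite degrees of freedom gave 4.7–5.3% in every scenario simulated. Sending unequal-variance data to Jonckheere-Terpstra instead gave 5.8%, 7.2% and 11.1% for sizes 200/100/46 with SDs 1/1.25/1.5, 1/1.5/2 and 1/2/3, so that route is only a partial repair.

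**The case against.** The best defence concerns consequence. The trend test is an addition to the overall comparison. It sits in a general catalogue of tests, and no ordinal predictor is named. The sample size rests on a correlation between two quantitative changes. The effect of pH is estimated by linear regression on continuous change in pH, categorical predictors enter that regression as indicator variables, and equal variance there is checked through residuals. All of this stands. A reader might infer that the study's main claim about pH and cardiac function carries an 11–22% false-positive rate; the documents do not support that, because nothing in them bands pH into ordered groups or uses a trend test for a primary objective.

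A second defence is that 11–22% is the adverse end. It needs markedly unequal groups with the smaller ones more variable, the unweighted form of the test and no normality gate. This also stands, and the figures should be read only with those conditions. A reader might equally infer that equal group sizes remove the problem; the 8.8% for SDs 2/1/2 shows otherwise.

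A third defence is that the trend test silently inherits the ANOVA conditions. The text does not say so. If it did, normal data with unequal variances would have no trend test at all, and the sentence would still need amending.

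**Conclusion.** The inconsistency is in the text and does not depend on any calculation: one paragraph requires equal variances for ANOVA and then drops the requirement for the ANOVA trend test. The residual checks in section 8 are stated for regression and do not repair it.

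The numerical effect is conditional on the assumed sizes and SDs and on a pooled error term, and it can go in either direction: inflation when the smaller groups are the more variable, conservatism when the larger ones are. It bears on supplementary trend P values only. Priority: minor.

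**What to change.** In all three copies (Study Summary, section 4, section 8), state that for normally distributed data the trend test is a linear contrast of group means with separate group variances and Welch-Satterthwaite degrees of freedom, and give the scores or weights used. Keep Jonckheere-Terpstra for non-normal data. Merely adding a variance condition that leads to Jonckheere-Terpstra is not enough, as the figures above show.

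The cost is one sentence in three places, and the calculation needs only group means, variances and sizes. The loss of power when variances really are equal is small. For sizes 200/100/46 the Satterthwaite degrees of freedom are (1/200 + 1/46)²/[(1/200)²/199 + (1/46)²/45] ≈ 67, so the critical value rises from 1.97 to 2.00. For an effect that gives about 80% power, Φ(2.80 − 1.97) = 0.797 becomes Φ(2.80 − 2.00) = 0.788, a loss of about one percentage point.

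### A normality pre-test on the study data chooses the test and effect measure for the primary relationship, and the stated 80% power is not established for Spearman, one of its two outcomes

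*Combined protocol and SAP*

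**What the plan says.** Section 4 (Study Design, Calculation of the sample size) takes the primary objective to be the relationship between change in pH and change in cardiac contractility. With two-sided alpha 5% and power 80%, it assumes "a minimum ratio that has an estimated clinical significance with a correlation coefficient of 1.5", and "a bilateral estimate of sample size of 346 subjects is obtained". It does not say whether the coefficient is Pearson's or Spearman's.

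Section 8 (Statistical Methods) sets the analysis rule; the Study Summary and section 4 carry the same text. Two quantitative variables are related by Pearson's r under normality, "or with the nonparametric correlation coefficient ρ of Spearman if normality is not met". The pre-test is named: "Normality is assessed with the Kolmogorov-Smirnov test with the Lilliefors significance correction for large samples", with Shapiro-Wilk for small samples. The plan does not define large or small, and does not say whether one or both variables must pass.

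The two-group rule works the same way. If normality fails, "the comparison of two means is made with the non-parametric Mann-Whitney U test".

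Section 8 also plans a multivariable linear regression of change in cardiac output on change in pH (lowest to highest), with its conditions checked on the residuals.

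**The concern.** Pearson's r and Spearman's rho are different quantities, as are a difference in means and the rank comparison made by Mann-Whitney. Mann-Whitney does not in general compare means, so the second switch changes the question as well as the method. Under this rule the primary effect measure is unknown until the data have been tested. Two analysts could also reach different choices, because the rule leaves open which variables must pass and which normality test applies.

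With several hundred patients, a normality test reacts to modest skew, at which inference on means and slopes is usually already robust. The switch could therefore be triggered where it is not needed, and the sample size makes no stated allowance for a rank test.

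**Working it through.** **Inputs.** From section 4: two-sided alpha 0.05, power 0.80, N = 346, 5% loss, total 363. The coefficient is printed as 1.5, which is impossible for a correlation. It is read here as 0.15, an assumption. The documents give no distribution, SD or skewness for either variable, so every shape below is assumed.

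**Step 1: reproduce 346.** The Fisher z formula for a Pearson correlation is N = ((z₀.₉₇₅ + z₀.₈₀)/atanh(r))² + 3. With r = 0.15:

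- atanh(0.15) = 0.1511
- N = ((1.960 + 0.842)/0.1511)² + 3 = 346.6

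A bias-corrected version gives 345.6, a t-based version 342.9, and a one-sided test 274. The stated 346 is therefore the two-sided Pearson figure. Power at 346 is Φ(0.1511 × √343 − 1.960) = 79.9%. The loss allowance is 5% of 346 = 17.3, taken as 17, and 346 + 17 = 363.

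**Step 2: Spearman at 346, by formula.** Power = Φ(atanh(ρₛ) × √(343/v) − 1.960), where v is 1, 1 + ρₛ²/2 (Bonett-Wright) or 1.06 (Fieller).

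- Target ρₛ = 0.15: power 79.9%, 79.5%, 77.6%; N for 80% is 347, 351, 368. With v = 1 this is simply the Pearson formula.
- Target Pearson r = 0.15 under bivariate normality, so ρₛ = (6/π) × asin(0.075) = 0.143: power 76.2%, 75.8%, 73.8%; N for 80% is 380, 384, 403.

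**Step 3: how often the pre-test would switch.** Simulated Lilliefors rejection at n = 346:

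| Assumed shape | Rejection |
|---|---|
| Gamma, skewness 0.5 | 62% |
| Gamma, skewness 0.8 | 95% |
| Lognormal (sigma 0.25), skewness about 0.8 | 92% |
| Gamma, skewness 1.0 | over 99% |
| Simulated range of 12 blood gases, skewness 0.66 | 89% |
| Simulated range with widely varying stay, skewness 0.14 | 6% |

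**Step 4: power at 346 where the data are skewed.** There were 8,000 simulated samples per row, and 20,000 for the first row.

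| Setting | Pearson | Spearman |
|---|---|---|
| Bivariate normal, r = 0.15 | 80% | 76% |
| Exponential pH change, linear effect, normal errors | 79% | 64% |
| Lognormal (sigma 0.5) pH change, linear effect, normal errors | 80% | 68% |
| Gamma(4) pH change, linear effect, normal errors | 80% | 73% |
| Gamma(4) pH change, linear effect, gamma(4) errors | 80% | 82% |
| Both lognormal (sigma 0.5), underlying normal r = 0.15 | 69% | 76% |
| Both lognormal (sigma 0.5), Pearson r = 0.15 | 78% | 84% |
| Both lognormal (sigma 1.0), Pearson r = 0.15 | 75% | 98% |

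**Step 5: the two-stage rule as a whole.** Run as pre-test then coefficient, it kept type I error near 5%. In the linear model with normal errors its power was about 74% (gamma(4) pH change) and 64% (exponential pH change).

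**The case against.** The strongest reply has three parts.

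1. **Spearman is used only when normality fails.** The 76% assumes bivariate normality, where the rule would mostly keep Pearson. In skewed data Spearman beat Pearson in four of the seven settings above. This stands. A reader might infer that 346 patients are too few whenever Spearman is used; the documents do not support that, because power in the relevant situation can lie on either side of 80%.

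2. **The documents do not say that the change in pH is skewed.** This also stands. A highest-minus-lowest difference cannot be negative, so right skew is plausible. But the simulated ranges gave rejection rates of both 89% and 6%. A reader might infer that the plan will usually end in Spearman; that is conditional on a distribution the documents never give.

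3. **A regression is already planned, with residual checks and no switch to ranks.** This stands only in part. Its response is change in cardiac output, whereas the sample size concerns contractility, and the plan nowhere makes the regression the primary analysis. The unequal-variance t test is likewise already in the plan, but only after normality and variance checks.

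It is also fair to say that section 4 does not name Pearson; if the target was ρₛ = 0.15, the shortfall is about 0 to 2 points.

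**Conclusion.** The concern holds in a limited form. The plan leaves the test and effect measure for its powered relationship to a normality test on the study data, and its 80% power is not established for one of the two possible outcomes.

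If the change in pH has skewness 0.5 to 0.8, a switch at 346 patients is likely (about 60% to over 90%). Spearman power may then be about 64% to 74% (skewed pH change, linear effect, normal errors) or as high as 98% (both variables skewed). These figures rest on reading 1.5 as 0.15 and on assumed shapes. They do not show that the study is underpowered, and no inflation of type I error was shown. The defect is an effect measure and a power that are not fixed in advance. It should be corrected, and the impossible coefficient with it.

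**What to change.** In section 8, and in the matching text of section 4 and the Study Summary:

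- Delete the normality pre-test for the primary relationship.
- Name one primary analysis and one effect measure in advance. An example is the already planned regression slope for change in pH on one named cardiac response, with heteroscedasticity-robust (HC3) or bootstrap confidence intervals. Section 4 and the regression must name the same response.
- Keep Spearman's rho as a sensitivity analysis, reported whatever the distribution.
- Use the unequal-variance t test where means are compared, and stop describing Mann-Whitney as a comparison of means.
- Correct the printed coefficient of 1.5, and state that the 80% refers to the Pearson or regression test.
- Do not add a power of about 76% for Spearman unless its bivariate-normal condition is stated beside it.

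The cost is SAP wording only, with no extra patients or data. The trade-off is a possible loss of power against Spearman if the data prove heavy-tailed.
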